1.5.3 Systematic review on the timing of RRT initiation in AKI

We have performed a systematic review and meta-analysis examining timing of RRT initiation in critically ill patients with AKI.¹³ We included controlled studies that specifically focused on adult critically ill patients with AKI receiving RRT where timing was evaluated and mortality was reported. We identified 15 unique studies for inclusion (2 randomized trials, 4 prospective cohort studies, and 9 retrospective cohort studies) published between 1999 and 2010. Overall study quality was generally low. In a pooled analysis, early initiation of RRT was associated with a significantly reduced odds of death (OR 0.45; 95% CI, 0.28-0.72) when compared to delayed or late RRT initiation amidst important heterogeneity ($I^2 = 78\%$). We believe that these findings, while limited in inference due to the observed heterogeneity, confirm equipoise for a prospective randomized trial evaluating whether accelerated/early initiation compared to a conservative strategy for RRT initiation in critically ill patients with AKI can impact patient survival and kidney recovery.

1.5.4 Completion of the STARRT-AKI pilot trial confirming the feasibility and safety of the protocol

We completed a CIHR-funded 12-centre RCT that confirmed the feasibility and safety of our protocol.^{40,41} We identified 132 individuals who met all the eligibility criteria and enrolled 101 individuals (77%; pre-specified target > 50% for enrollment of eligible patients). The median time from eligibility to initiation of RRT was 7.4 hours in the accelerated arm and 3/48 (6%) participants commenced RRT beyond the specified 12-hour window for that treatment arm. In

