- The secondary analyses will not be adjusted for multiple testing; however, the results of all statistical testing will be reported according to the American Statistical Association guidelines to provide the necessary context for interpretation.¹⁷
- All estimates of treatment effect will be accompanied by 95% confidence intervals (CI).
- All analyses will be performed using the R software package (R Core Team, 2008; www.R-project.org).

Interim analyses and the Data Safety Monitoring Board

An independent DSMB will review unblinded data to examine recruitment rate, patient characteristics, randomisation compliance, treatment compliance, completeness of data, outcomes and adverse events on three occasions (following the completion of 90-day follow-up for the 716th, 1432nd and 2150th patient, respectively). The DSMB charter is available at: <https://www.ualberta.ca/critical-care/research/current-research/starrtaki/documents.10>

Analysed datasets

All main analyses will be performed on the ITT population dataset. For these analyses, all patients will be analysed according to the group to which they were randomised; however, any randomised patient found to have not fulfilled eligibility criteria based on data available at the time of initial assessment (ie, randomised in

error) will be excluded following independent adjudication by two investigators who will be blinded to outcomes.¹⁸

Trial profile

The flow of patients through the trial will be shown in a Consolidated Standards of Reporting Trials (CONSORT) diagram (Figure 1).¹⁹ The figure will provide a summary of the number of patients screened, the number of patients who fulfilled eligibility, the number of patients who were excluded and the reason(s) for exclusion.

Patient characteristics and baseline comparisons

- A description of baseline characteristics will be presented by treatment allocation, as outlined in the proposed Table 1 .
- Categorical variables will be summarised with frequencies and percentages. Percentages will be calculated according to the number of patients for whom data are available.

- Continuous variables will be summarised as means with standard deviation (SD) or medians with the interquartile range (IQR) (Q1 and Q3).

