- Baseline measures for all patients will be tabulated for the following variables: ▶ sociodemographics; ▶ admission characteristics; ▶ pre-existing comorbidities; ▶ primary diagnostic category; ▶ vital signs at the time of randomisation; ▶ laboratory data at the time of randomisation; ▶ baseline kidney function; ▶ severity of illness at the time of randomisation; and ▶ organ support (eg, mechanical ventilation, vasopressor therapy) at the time of randomisation.

The information on the proposed additional figures and supplementary tables and figures is included in the online Appendix (available at cicm.org.au/Resources/Publications/Journal).

Analysis of adherence to timelines for randomisation and renal replacement therapy initiation

Compliance with randomisation will be reported and defined as the proportion of all enrolled patients who are randomised within 12 hours of fulfilling eligibility. Compliance with treatment allocation will also be reported overall and separately for both the accelerated and standard groups. In the accelerated group, compliance will be defined as the proportion of patients initiating RRT within 12 hours of meeting all eligibility criteria. In the standard group, compliance will be defined as the proportion of patients who initiated RRT more than 12 hours from the time of eligibility or who did not receive RRT at any time during the follow-up period.

Protocol deviations

Protocol deviations will be summarised as the number of deviations by type (eg, randomisation of ineligible patient, failure to adhere to randomisation timeline, failure to adhere to allocated intervention). All deviations will be listed and will be adjudicated by the principal investigators

Table 1. Baseline characteristics by treatment allocation*

Characteristic	Accelerated strategy	Standard strategy
	(N = xxxx)	(N = xxxx)
Age (years), mean (SD)	xx.x ± x.x	xx.x ± x.x
Female sex, n (%/0)	xxxx (xx.x%)	xxxx (xx.x%)
Weight (kg), mean (SD)	xx.x ± x.x	xx.x ± x.x
Coexisting conditions, n (%/0)		
Hypertension	xxxx (xx.x%)	xxxx (xx.x%)
Diabetes mellitus	xxxx (xx.x%)	xxxx (xx.x%)
Heart failure	xxxx (xx.x%)	xxxx (xx.x%)
Coronary artery disease	xxxx (xx.x%)	xxxx (xx.x%)
Liver disease	xxxx (xx.x%)	xxxx (xx.x%)
Metastatic cancer	xxxx (xx.x%)	xxxx (xx.x%)
Hematologic malignancy	xxxx (xx.x%)	xxxx (xx.x%)
AIDS	xxxx (xx.x%)	xxxx (xx.x%)
SAPS II score at enrolment, † mean (SD) xx.x ± x.x	xx.x ± x.x	SOFA score at enrolment, † mean (SD) xx.x ± x.x
Admission type, n (%/0)		

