Evaluation of heterogeneity in treatment effect Death at 90 days will also be analysed across baseline predicted risk of death using the SAPS II score ²¹ This analysis will be assessed by adding an interaction between treatment and SAPS II in the fully adjusted model described earlier.

Subgroup analyses

We will evaluate the effect of allocated treatment on the primary outcome across the following a priori defined subgroups by means of interaction terms in the adjusted model and displayed in a forest plot: ● patient sex; ● baseline eGFR, ● baseline SAPS II score; ● primary reason for ICU admission surgical versus medical; ● sepsis; and ● geographic region (eg, North America, Europe, Australia/ New Zealand, Asia/South America etc).

Exploratory analyses of the primary outcome We will further evaluate the primary outcome with the following exploratory analyses:

- We will examine the effect of the allocated treatment on the primary endpoint in a per-protocol population, defined by omitting patients with a protocol violation due to crossover to the opposite allocated treatment to which they were randomised.

- We will examine the effect of the treatment on the primary endpoint in a modified ITT (mITT) population. The mITT population will be defined as an "as treated" population, whereby patients with a protocol violation will be analysed in the treatment arm that reflects the RRT initiation strategy that was received.
- To further inform the interpretability of the main primary analysis, we will examine the utility of a Bayesian analysis approach, across a range of plausible reference and data-driven priors, to provide estimates of the posterior probability of any mortality benefit (using both relative risk and absolute risk reduction), of an accelerated compared with standard strategy for RRT initiation in critically ill patients with severe AKI ²²
These proposed exploratory analyses may be reported after the publication of the main trial findings.

Additional analyses of mortality

The analysis of all-cause mortality described in the main analysis will be replicated to compare the proportion of patients who died in the ICU, before hospital discharge, and at 28 days after randomisation, respectively. No additional adjusted or subgroup analyses will be performed on these endpoints.

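### The exploratory set labelled 'modified ITT' is an as-treated set: a non-randomised comparison with no adjustment named and incomplete reassignment rules

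*SAP*

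**What the plan says.** The main analyses respect randomisation. Under Analysed datasets the SAP states: "All main analyses will be performed on the ITT population dataset". Patients in that set are analysed in the arm to which they were randomised. One group is removed after blinded adjudication, namely "any randomised patient found to have not fulfilled eligibility criteria based on data available at the time of initial assessment".

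Under Exploratory analyses of the primary outcome, two further populations are described:

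- A per-protocol set, "defined by omitting patients with a protocol violation due to crossover to the opposite allocated treatment to which they were randomised".
- A second set, introduced with "We will examine the effect of the treatment on the primary endpoint in a modified ITT (mITT) population". The next sentence defines it as as-treated, so that "patients with a protocol violation will be analysed in the treatment arm that reflects the RRT initiation strategy that was received".

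The SAP adds: "These proposed exploratory analyses may be reported after the publication of the main trial findings".

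Three other places bear on the point:

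- The SAP section on adherence to timelines sets the accelerated-arm criterion: "In the accelerated group, compliance will be defined as the proportion of patients initiating RRT within 12 hours of meeting all eligibility criteria". For the standard group, compliance means starting RRT after 12 hours or never receiving it.
- Protocol section 2.14 says that the patient's changing clinical needs take priority over adherence and that some crossover is therefore unavoidable.
- The SAP's Adjusted sensitivity analysis specifies a model for 90-day mortality with baseline covariates such as age, sex, eGFR, SAPS II, surgical status and sepsis.

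**The concern.** The label and the definition point in opposite directions. By the SAP's own account, an ITT analysis keeps patients in their randomised arm. The set named as a modification of ITT gives up exactly that property and sorts violators by what happened after randomisation. In usual terminology, a modified ITT set drops a few patients for reasons fixed at baseline. That is closer to what the SAP's main ITT set already does by removing patients randomised in error, so the label could also be taken for the wrong set.

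In an open-label trial where crossover may follow clinical state, patients who cross over can differ in prognosis from those who do not. Moving them, with their deaths, into the other arm can create or hide a difference. The bullet names no adjustment.

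The rule is also incomplete in two respects:

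- The per-protocol bullet limits violations to crossover, but this bullet does not. The SAP's Protocol deviations section also lists randomisation of an ineligible patient and late randomisation, and neither implies that the other strategy was received.
- Nothing says where an accelerated-arm patient belongs who dies or recovers before RRT can start.

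At stake is the reading of later tables or a later paper that may carry only the short label. A reader could take the result as nearly randomised support for, or contradiction of, the primary analysis.

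**Working it through.** **Inputs from the documents**

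- Standard-arm 90-day mortality 40%, 34% under the target effect, two-sided 5%, power 90% (Protocol 2.9; SAP Sample size and Analysis principles).
- Pilot violations: in the accelerated arm, "3/48 (6%) participants commenced RRT beyond the specified 12-hour window for that treatment arm", that is 3/48 = 6.25%. In the standard arm, none started within 12 hours (Protocol 1.5.4 and 2.14).
- A combined 3% for crossover and dropout (Protocol 2.9), to which the SAP adds loss to follow-up.

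**Assumed input**

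The documents give no mortality for violators. Values of 20%, 40% and 60% are assumed.

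**The plan's own figure**

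With pooled variance and no continuity correction:

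n = [1.960·√(2 × 0.37 × 0.63) + 1.2816·√(0.40 × 0.60 + 0.34 × 0.66)]² / 0.06² = 1,359 per arm

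This matches the protocol. Taking the protocol's 2,780 after interim analyses as given, 2,780/0.97 = 2,866, or 1,433 per arm. Nothing here disputes those figures.

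**Effect of reassignment when there is no true effect**

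Let both randomised arms have mortality p = 0.40. Let a fraction f of the accelerated arm, with mortality m, be moved to the standard arm.

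- Accelerated as treated: (p − f·m)/(1 − f)
- Standard as treated: (p + f·m)/(1 + f)
- Difference: 2f(p − m)/(1 − f²)

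Example with f = 0.0625 and m = 0.20:

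- Accelerated: (0.40 − 0.0125)/0.9375 = 0.4133
- Standard: (0.40 + 0.0125)/1.0625 = 0.3882
- Risk ratio 1.065, difference +2.5 points

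| Fraction moved | Violator mortality (assumed) | Accelerated | Standard | Risk ratio | Difference (points) |
|---|---|---|---|---|---|
| 6.25% | 20% | 0.4133 | 0.3882 | 1.065 | +2.5 |
| 6.25% | 40% | 0.4000 | 0.4000 | 1.00 | 0 |
| 6.25% | 60% | 0.3867 | 0.4118 | 0.939 | −2.5 |
| 3% | 20% | 0.4062 | 0.3942 | 1.03 | +1.2 |
| 3% | 40% | 0.4000 | 0.4000 | 1.00 | 0 |
| 3% | 60% | 0.3938 | 0.4058 | 0.97 | −1.2 |

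The shift is zero when violators have the same risk as everyone else, and its sign follows their prognosis. For scale, the design effect is 6 points.

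**The case against.** The strongest reply is that the SAP hides nothing. It uses the term as-treated in the very sentence that defines the set, places the analysis under an exploratory heading, says only that it may be reported later, and gives it no row in Table 2. The main analyses are ITT. All of this stands, and it confines the point to labelling, definition and adjustment of one exploratory analysis.

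Four stronger readings are tempting, and the documents do not support them.

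- *That the analysis carries a false-positive rate of about 28%.* This is the chance of nominal significance at the two-sided 5% level with 6.25% moved and violator mortality of 20% or 60%. It depends on that assumed mortality and falls back to the nominal level at 40%. It also presumes a decision rule, whereas the SAP attaches none to this analysis and avoids formal testing of secondary analyses.
- *That an accelerated-arm patient who dies or recovers before RRT is counted as standard.* The SAP does not say so. Its never-received-RRT wording defines compliance for the standard group only. The supportable statement is that the classification is undefined.
- *That the pilot documents that route.* Its three violators started RRT late, so they had neither died nor recovered before starting. The 3% figure mixes crossover with dropout and so is not a rate of moved patients either. Both fractions only set a scale.
- *That every late start reflects prognosis.* The 12-hour window also covers consent (Protocol 2.3.2), so some delays may be logistical.

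A further reply is that silence in the bullet does not rule out adjustment. That is true, but the subgroup text in the SAP names the adjusted model explicitly and this bullet names none, so the choice is left open.

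**Conclusion.** The point holds as a defect of an exploratory analysis. A set defined by treatment received is labelled as a form of ITT, its reassignment rule is incomplete, and no adjustment is named for a comparison that randomisation no longer protects. That it is open to confounding follows from the protocol's own account of why crossover occurs. Neither the direction nor the size of any bias can be established from the documents.

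The illustrative shifts of up to 2.5 points either way rest on four assumptions: no true effect, 40% mortality in both arms, movement out of the accelerated arm only, and violator mortality 20 points below or above the average. A reader might infer that the trial's conclusion is threatened. It is not: the primary ITT comparison, sample size and alpha do not depend on this analysis.

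**What to change.** Settle the following in the SAP before database lock:

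1. Drop the mITT label and use as-treated in all tables and text.
2. State that it is not a randomised comparison.
3. Limit reassignment to crossover in RRT timing, in line with the per-protocol bullet, and state how an accelerated-arm patient who dies or recovers without starting RRT within 12 hours is classified for this analysis.
4. Fit it with the baseline-covariate model from the Adjusted sensitivity analysis, noting that this reduces confounding but cannot remove what arises from events after randomisation.

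Deleting the analysis is an acceptable alternative. A complier-average estimate, which keeps the randomised arms, could be added with its assumptions stated, but it is optional. It requires allocation to act only through starting RRT within 12 hours, which is hard to defend when pilot standard-arm patients who started RRT did so at a median of 31.6 hours and others never started. At 6.25% non-compliance in the accelerated arm and none in the standard arm it would also change little: 6.0/0.9375 = 6.4 points.

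The cost is a few sentences of SAP text and minor programming. Sample size, power and alpha do not change.
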